Participant Participation Duration: The participation duration is about 80-90 minutes (including 30 minute-long monitoring time) in a single visit.

Estimated Time to Complete Enrollment: 15 months

Schematic of Study Design:

Prior to
Enrollment

Total 25: Obtain informed consent. Screen potential subjects by inclusion and exclusion criteria; obtain history, document.

Visit 1
On the day
Of a Biopsy

Conventional ultrasound imaging will be performed to examine the tumor followed by CEUS exam. Before collecting CEUS data, Definity will be administered IV and the acoustic settings will be optimized using a built-in software in a modified Logiq E9 or E10 scanner. The 3D SHAPE data will be collected using the determined acoustic settings during the infusion. Then, we wait for the clearance of Definity and another set of SHAPE data will be collected without Definity keeping the same acoustic settings.

The subject will have local anesthesia procedure and IFP will be measured from the breast tumor and its surrounding tissue using an 18G single-use needle connected to Stryker pressure monitoring system. The measurement procedure will be guided by ultrasound imaging. The measurements will be documented as well as their locations.

Compare the results from 3D
SHAPE data to IFP measurements
and find the correlation

1 Introduction

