6.4 End of Treatment Study Procedures

We will collect the results from a breast biopsy obtained as standard of care.

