11.2 Analysis Plans

Radio frequency (RF) data from 3D SHAPE will be transferred to a PC for off-line analysis. 3D RF data from SHAPE will be composed of multiple 3D volumes (5 to 21 volumes) over time. Each 3D volume will consist of multiple 2D data sets (about 79 slices), which will be collected in the elevational direction. All data processing will be

performed using Matlab (R2015b; Mathworks, Natick, MA). Two regions of interest (ROI) will be selected in each elevational plane for SHAPE: one within the tumor and the other in the surrounding tissues (available top and/or bottom region of tumor). The ROIs of the tumor and surrounding area will be selected as a free form on the images generated from RF data (i.e., raw data before post-processing for on-screen display). The ROIs will be selected by the sonographer or radiologist. Then, a Fast Fourier Transform will be computed for each A-line within the ROI to obtain the frequency spectrum. The maximum magnitude from the resultant frequency spectrum will be extracted from each pre- and during infusion data sets and the ratio will be calculated for each ROI. If both top and bottom regions are selected as a surrounding area ROI, then the ratios will be averaged to one value. Finally, the obtained subharmonic signal ratios from the tumor and the surrounding area will be compared to the direct IFP measurements. Pearson's correlation coefficients will be computed between SHAPE results and direct IFP measurements by Stryker compartment pressure monitoring system. These data will also be rigorously analyzed for agreement using Bland-Altman analysis (Bland & Altman, 1999) among tumor and healthy tissue samples. To explore if the relationship between SHAPE results and IFP is confounded by or might depend on study variables collected (e.g.'s, patient characteristics, tissue/tumor characteristics, etc.) linear mixed effects or generalized estimating equations modeling will be used. Generalized linear mixed logistic or GEE logistic modeling of tumor vs. non-tumor samples will be used to explore the potential for using SHAPE results as a novel functional predictor of breast tumor malignancy. Additionally, the subharmonic signal ratio from the tumor will be used to predict the malignancy of breast tumor using a biopsy result as a gold standard. The Mann-Whitney or Student's t-test will be performed depending on the distribution of the results.

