11.3 Sample Size Considerations

The aim of the study is to determine the correlation between SHAPE results and direct measurements of IFP. The aim is to get significant result ($p < 0.05$) with sufficient power (80%) to detect at least correlation coefficient of 0.5-0.6. Therefore, the required sample size for this study is 19 -29 based on the formula for calculation is based on two-tailed test [Guenther 1977]. Thus, we chose 25 patients as our sample size.

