15.2 Data Capture Methods

All patient data will be captured electronically via excel file in a password protected computer and image and 3D SHAPE data will be stored in the secured computer hard drive. Image and 3D SHAPE data will be de-identified. Copies of study documents will have personal identifying information retracted and replaced with study patient ID number. Originals of the study documents with personal identifying information will be retained at TJU. All this information will be available for audit. In addition, de-identified study data may be shared with study co-sponsors GE Healthcare and Lantheus Medical Imaging.

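### Section 11.2 does not mask the ROI reader to IFP or biopsy, nor lock contours before data are merged, so either reference standard can influence the SHAPE value

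*Combined protocol and SAP*

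**What the plan says.** Under 11.2 Analysis Plans, RF data go to a PC for off-line analysis. A tumor ROI and a surrounding-tissue ROI are chosen in each elevational plane, with about 79 slices per volume. The contours "will be selected as a free form on the images generated from RF data", and "The ROIs will be selected by the sonographer or radiologist". The surrounding tissue may be taken above the tumor, below it, or both. The spectrum, its maximum and the pre-infusion/during-infusion ratio are computed from those contours.

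The ratio is then used in two ways. It is correlated with the Stryker IFP, and section 2.2.1 counts a Pearson coefficient above 0.5 as success. It is also used to predict malignancy, with biopsy as the reference (2.2.2 and 11.2).

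On timing, section 6.3 places the IFP readings at the same visit as the contrast scan. The Schematic of Study Design adds: "The measurement procedure will be guided by ultrasound imaging". On histology, section 6.4 says: "We will collect the results from a breast biopsy obtained as standard of care". Section 3.5 schedules SHAPE analysis in Quarters 2 to 5, alongside enrollment.

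The study is open-label (3.1). The nearest thing to a safeguard is in 15.2: "Image and 3D SHAPE data will be de-identified". The QA reviews in sections 5.9 and 13 do not mention masking.

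**The concern.** The index test depends on a hand-drawn boundary, and the plan allows that boundary to be drawn by someone who knows the answer it will be compared with. Section 1.2 tells the team which direction to expect: higher pressure, lower subharmonic signal. A contour that takes in slightly more or less bright tissue moves the ratio, and a reader who knows the pressure or the histology can lean without intending to.

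Success is a point-estimate threshold with no confidence limit attached, so a modest shift near the cut-off changes the conclusion. The malignancy analysis is exposed in the same way through the biopsy result. With no locked contours, a reported |r| just above 0.5 could not afterwards be separated from reader influence.

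**Working it through.** **1. The plan's own figure.** Section 11.3 gives 19-29 patients for r = 0.6 to 0.5 at 5% significance and 80% power, and says "the formula for calculation is based on two-tailed test". By Fisher's z, n = ((1.960 + 0.842)/atanh(r))² + 3. This gives 29.01 for r = 0.5 and 19.34 for r = 0.6. The exact distribution of r gives 29 and 19. The stated range reproduces, and masking does not affect it.

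**2. How sensitive the success rule is.** With n = 25 and no reader influence, the exact P(r > 0.5), for r signed in the hypothesised direction, is 13.5% at true r = 0.3, 29.0% at 0.4 and 52% at 0.5. The rule is steep in the region where a pilot is likely to land.

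**3. Contour model.** The documents give no figure for ROI variance or reader drift, so every input except n = 25 and the inverse direction is an assumption:
- SHAPE = √(1−f)·S₀ + √f·e, where S₀ has correlation −0.3 with IFP, e is the contour effect, and f is the share of SHAPE variance due to ROI choice (10% to 20%).
- Each patient has three plausible contours, that is, three draws of e.
- A masked reader takes one at random. The expected |r| is then 0.3 × √0.9 = 0.285 to 0.3 × √0.8 = 0.268.
- A leaning reader takes the contour believed to lower SHAPE when IFP is high and raise it when IFP is low. The belief is either exact, or correlates 0.5 with the contour's true effect.

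Simulated P(|r| > 0.5), with ranges over f = 10% to 20%:

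| Reading | Belief correlates 0.5 | Always the most favourable contour |
|---|---|---|
| Masked | 10-12% | 10-12% |
| Leans in half the patients | 17-18% | 25-29% |
| Leans in all patients | 25-29% | 43-59% |

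Milder inputs give less. With belief correlation 0.3 and leaning in half, P is about 14-15%. With f = 2-5%, belief correlation 0.5 and leaning in half, it is 15-17%, against about 13% masked. If the true correlation is zero, leaning in half the patients yields only about 2-3%, even with the most favourable contour always chosen.

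**4. A second model.** Let the reader add d SD of SHAPE per SD of IFP in the hypothesised direction. Then ρ_eff = (ρ + d)/√(1 − ρ² + (ρ + d)²). For ρ = 0.3:
- d = 0.1: 0.4/√(0.91 + 0.16) = 0.387, so the exact P(r > 0.5) rises from 13.5% to 26.4%.
- d = 0.2: 0.5/√(0.91 + 0.25) = 0.464, so P is 43.1%.

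If tumor and surrounding values are pooled (50 points, ignoring within-patient correlation), P goes from 5% to 17% and 39%.

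**5. Sign.** Step 3 scores |r|. If the inverse sign is kept and the rule is read literally as r above +0.5, P is about 0 in every row of the table, leaning or not.

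**The case against.** The strongest reply concerns direction. A reader might infer that leaning always pushes the trial toward success. The documents do not support that: section 1.2 expects an inverse relation, 2.2.1 asks for a coefficient above 0.5 without mentioning sign, and 11.2 does not say which way the ratio is formed. If the ratio keeps the inverse sign, leaning moves r toward −0.5, away from the written rule. This stands, and the point is conditional on it.

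Size comes next. A reader might take 25-29% or 43-59% as estimates. They are upper ends, requiring a reader who always finds the best of three contours. Under 11.2 the contour comes first and the spectrum and ratio follow, over many slices, so the reader must guess each contour's effect and also judge whether the patient's IFP is high or low for the cohort. This stands too, and is why the imperfect-reader column is shown.

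A reader might also infer that the person who draws the ROI is the person who guided the needle. The documents name no operator for the pressure measurement; they say only that it is ultrasound-guided. Shared staff is possible but not stated.

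Finally, 15.2 de-identifies the image and SHAPE data and describes their storage separately from the patient data file. That is some barrier, but it is a privacy step. In a single-site study of 25 patients, a reader who saw the case could recognise it, and nothing withholds the results.

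None of these replies supplies a masking or locking statement.

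**Conclusion.** The gap is real. The plan lets the IFP reading, and possibly the biopsy result, be known when the contours that define SHAPE are drawn, and it contains neither masking nor a contour lock. Both the primary correlation and the malignancy analysis are open to influence from their reference standards.

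Whether that influence helps the trial succeed depends on a sign convention the plan leaves open. Its size is unknown. On the assumptions shown, P(|r| > 0.5) rises from about 10-12% to 17-18% with an imperfect reader leaning in half the patients, with an upper bound of 25-29%. For leaning in all patients the corresponding figures are 25-29% and 43-59%. The effect matters most when the true correlation is weak to moderate. The documents show that drift is possible, not that it will occur. This should be corrected before contours are drawn; the sample size stands.

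**What to change.** Add to 11.2:
- The ROI reader is one of the existing sonographers or radiologists, works from coded, de-identified RF files, and has no access to IFP or biopsy results. Where staffing allows, the reader was not present at that patient's pressure measurement.
- Contours are saved and locked before SHAPE values are merged with IFP and histology.
- Reading may be done in batches, in random order within each batch, during the analysis quarters of section 3.5.

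In 2.2.1 and 11.2, state how the ratio is formed and whether success means |r| above 0.5 or a positive r under that orientation.

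The cost is a short paragraph, a file-locking step, some scheduling of batches, and a limit on who may draw a given patient's ROI. The documents do not describe staffing, so whether someone absent from every measurement is available has to be checked locally; hence the qualifier. Patient procedures and sample size do not change.

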1.2 Rationale for the Proposed Study

The IFP of breast tumors can be directly measured invasively using a wick-in-needle (WIN) technique, which employs a catheter connected to a transducer to record the pressures [Taghian et al. 2005]. However, this invasive method is difficult to apply in patients and not standard of care. Contrast-enhanced ultrasound (CEUS) has shown potential to estimate tumor IFP in animals [Halldorsdottir et al. 2014]. CEUS utilizes microbubbles, which not only enhance the backscattered signals, but at higher acoustic pressures also act as nonlinear oscillators producing multiple harmonics of the fundamental frequency. Microbubbles can also act as pressure sensors, due to the difference in compressibility between the bubble and the surrounding medium. Our group has developed the fundamental concept of subharmonic (half of fundamental frequency) aided pressure estimation (SHAPE) using CEUS and demonstrated its potential to non-invasively measure IFP [Halldorsdottir et al. 2014]. The SHAPE method estimates IFP using the inverse relationship between the CEUS signal magnitude at the subharmonic frequency and IFP. This inverse relationship varies with the applied acoustic pressure and an individual optimization of the acoustic setting for SHAPE is therefore needed [Shi et al. 1999]. Recently, we conducted a pilot study of 3D SHAPE's ability to monitor treatment response in women undergoing neoadjuvant chemotherapy (NAC) for locally advanced breast cancer (LABC) [Nam et al. 2017], showing that the subharmonic signal difference in the tumor relative to the normal tissue could predict treatment response after administration of 10% of therapy regimen (i.e., 1 cycle of neoadjuvant regimen). This study did not measure IFP directly, therefore the correlation between IFP and subharmonic signal magnitude has not been studied yet. Thus, in this

study, we will determine if the 3D SHAPE can estimate IFP in breast tumors and the surrounding normal breast tissue noninvasively.

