The use of an intravenous needle and the fluids given through the needle may cause minor discomfort, bleeding under the skin (bruise), fainting, and possible infection at the site of needle insertion. These risks are minimized by having nursing staff trained in placing IV lines perform these procedures in a safe, aseptic manner. The subjects' alternative is not to participate in this study and have only their scheduled clinical procedure(s) performed.

The invasive pressure measurement procedure (with 18G needle) has low risk similar to a stereotactic breast biopsy (mostly with 14G or larger needles). The risks includes: bruising and swelling of the breast, infection of the measurement site, and soreness at the needle injection. Also, there is low risk of infection and pain and they could be minimized by strict sterile technique and local lidocaine infiltration, respectively. The subjects' alternative is not to participate in the study.

1.4.2 **Benefits**

We do not expect any direct benefit for subjects enrolled in this study. The long-term benefits of this study will be the development of a noninvasive, safe, accurate IFP estimator. Additionally, it may lead to a novel functional predictor of malignancy in breast tumors.

2 **Study Objectives**

2.1 **Objectives**

This study is designed to compare the direct measurements of IFP in the breast tumor and its surrounding tissue with the values obtained from 3D SHAPE data (i.e., CEUS data).

2.1.1 **Primary**

The primary objective of the study is to determine if the 3D SHAPE results can be used to estimate IFPs in breast tumor and its surrounding tissue.

2.1.2 **Secondary**

The secondary objective of the study is to determine if the malignancy of breast tumor can be predicted by the 3D SHAPE results.

2.2 **Endpoints/Outcome Measures**

2.2.1 **Primary**

A Pearson's correlation coefficient above 0.5 will be considered a successful outcome.

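### Bland-Altman agreement is planned between a unitless signal ratio and a measured pressure, with no step that converts the ratio to pressure

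*Combined protocol and SAP*

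**What the plan says.** Section 11.2 builds the SHAPE result in these words: "The maximum magnitude from the resultant frequency spectrum will be extracted from each pre- and during infusion data sets and the ratio will be calculated". This is done for each region of interest, one in the tumor and one in the surrounding tissue. The plan then says "the obtained subharmonic signal ratios from the tumor and the surrounding area will be compared to the direct IFP measurements", and that "Pearson's correlation coefficients will be computed between SHAPE results and direct IFP measurements by Stryker compartment pressure monitoring system". The next sentence is "These data will also be rigorously analyzed for agreement using Bland-Altman analysis", among tumor and healthy tissue samples. No acceptable difference or precision target is given for the limits of agreement.

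The primary objective in section 2.1.1 is to "determine if the 3D SHAPE results can be used to estimate IFPs in breast tumor and its surrounding tissue". Section 2.2.1 defines success as a Pearson coefficient above 0.5. The Study Summary speaks of pressure estimates from SHAPE, but section 11.2 contains no step that yields one.

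Section 1.2 gives the physical basis: "The SHAPE method estimates IFP using the inverse relationship between the CEUS signal magnitude at the subharmonic frequency and IFP". It adds: "This inverse relationship varies with the applied acoustic pressure and an individual optimization of the acoustic setting for SHAPE is therefore needed". Of the earlier breast cancer pilot it says: "This study did not measure IFP directly, therefore the correlation between IFP and subharmonic signal magnitude has not been studied yet".

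**The concern.** Bland-Altman works on differences between paired measurements. The differences mean something only when both methods report the same quantity in the same units. Here one member of each pair is a pure number and the other is a pressure. The result would therefore change with the pressure unit, and it could not tell a good sensor from a useless one.

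What is at stake is the estimation objective. A correlation shows that two quantities move together. It does not show how far a SHAPE-based pressure would lie from the true one. Bland-Altman is the only analysis the plan names for agreement, and as written it cannot supply that information.

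**Working it through.** **The plan's own figures.** The documents give no Bland-Altman figure to reproduce. The nearby sample size does reproduce: the exact two-sided 5% test of a correlation at 80% power needs 19 patients for r = 0.6 and 29 for r = 0.5, which matches the 19-29 in section 11.3. It rests on correlation alone.

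**Inputs for the illustration.**
- IFP range 0 to 29 mmHg, taken as uniform (assumption). Section 1.1 cites a mean of 29 mmHg for invasive ductal carcinoma and values between -0.3 and 3.6 mmHg for normal, benign and noninvasive tissue.
- Ratio range 1 to 10, linear in IFP and free of noise (assumption; the documents give no calibration).
- Pressure unit mmHg, inferred from section 1.1. The unit of the Stryker reading is not stated.

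**Formula.** Let the ratio be S = a + b × IFP. The Bland-Altman difference is D = S - IFP = a + (b - 1) × IFP. Hence
- bias = a + (b - 1) × mean(IFP)
- SD(D) = |b - 1| × SD(IFP)
- limits = bias ± 1.96 × SD(D)

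There is no error term, so everything in the limits comes from a, b and the spread of IFP. For the uniform range, mean(IFP) = 14.5 and SD(IFP) = 29/√12 = 8.37.

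**Results.**

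| Sensor | Calculation | Bias | Limits |
|---|---|---|---|
| Perfect, ratio falls 10 to 1 (a = 10, b = -9/29) | 10 - 1.310 × 14.5; SD 1.310 × 8.37 = 10.97 | -9.0 | -30.5 to +12.5 |
| Perfect, ratio rises 1 to 10 (a = 1, b = 9/29) | 1 - 0.690 × 14.5; SD 0.690 × 8.37 = 5.77 | -9.0 | -20.3 to +2.3 |
| Useless, ratio constant at 5.5 (b = 0) | 5.5 - 14.5; SD 8.37 | -9.0 | -25.4 to +7.4 |
| Perfect falling sensor, pressure in kPa (1 mmHg = 0.133322 kPa) | 10 - 0.4437 × 14.5; SD 0.4437 × 8.37 = 3.71 | +3.6 | -3.7 to +10.8 |
| Perfect falling sensor, converted to mmHg by (10 - S) × 29/9 | D = 0 throughout | 0 | 0 to 0 |

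The useless sensor gets narrower limits than the perfect falling one. Changing only the unit moves the bias from -9.0 to +3.6. The error-free sensor shows perfect agreement once it is converted.

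**Sensitivity to the assumed calibration.** IFP was next spread evenly over 50 sites from -0.3 to 29 mmHg, with three other noise-free falling sensors:
- S = 3 - 0.05 × IFP: bias -12.1, limits -30.0 to 5.9
- S = 10 - 0.2 × IFP: bias -7.2, limits -27.7 to 13.3
- S = 20 - 0.1 × IFP: bias +4.2, limits -14.6 to 23.0

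The numbers move with the assumptions. The finding that the limits carry no information on error does not.

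**The case against.** **Bland-Altman is only a supporting analysis.** This stands. The success criterion (2.2.1), the main hypothesis (11.1) and the sample size (11.3) all concern correlation, and the Study Summary also words the primary objective as correlation. A reader might infer that the mismatch undermines the primary result; the documents do not support that. What remains is section 2.1.1, which asks whether SHAPE can be used to estimate IFP.

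**A conversion is implied by the term pressure estimates.** Perhaps it is intended, but none is written, and section 11.2 names the ratio as the quantity compared. Section 1.2 reports no calibration in breast cancer patients. A conversion chosen after the data are seen, and tested on the patients used to fit it, would make agreement look better than it is.

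**The mixed-effects or GEE models could give calibration error.** This stands in part. With IFP as outcome, a mixed model could yield a slope and a residual error in pressure units. A reader might therefore go too far in saying that calibration error could never be estimated under this plan. But those models are planned to explore confounding and dependence on other variables, the outcome variable is not named, and no prediction error is promised.

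**The ratio need not be inversely related to IFP.** This stands. Section 1.2 states the inverse relation for signal magnitude, while section 11.2 does not say which data set is the numerator. A pre/during ratio would rise as the signal falls. The point therefore rests on the unit mismatch, which applies in both directions, as the rising sensor shows.

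**Two sites per patient need not break independence.** This also stands. The wording of section 11.2 can be read as limits by tissue type, and section 6.3 plans a single reading at each site, so each set of limits would then hold one pair per patient. Pairing matters only if sites are pooled.

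**Conclusion.** The concern holds, limited to the agreement analysis. Followed as written, section 11.2 gives a bias and limits of agreement that cannot be interpreted, because they are set by the pressure unit and the spread of IFP. This is an error in the specified analysis, not a missing detail.

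It should be fixed before analysis, but it does not threaten the trial's stated success criterion or its 25 patients. The loss is that the estimation objective in section 2.1.1 has no valid agreement analysis.

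The limits of about -30 to +12 for a perfect sensor are an illustration that rests on the assumed ratio range of 1 to 10, linearity and uniform IFP. They do not predict what this trial would show. The qualitative conclusion needs only that the ratio is not expressed in pressure units.

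**What to change.** Amend section 11.2 in one of two ways, before the data are analysed.

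1. **Keep agreement.**
   - State the numerator and denominator of the ratio and the scale on which it enters the model.
   - Prespecify a calibration model of IFP in mmHg on the SHAPE ratio.
   - Obtain predicted IFP for each patient from a model fitted without that patient, leaving out both sites together.
   - Apply Bland-Altman to predicted minus measured mmHg, separately for tumor and surrounding tissue. Use limits that account for pairing only if sites are pooled.
   - Report the cross-validated prediction error.
2. **Drop agreement.** Delete the Bland-Altman analysis and limit the conclusion to correlation.

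The scale has to be chosen with care. For the linear falling sensor above, a straight-line calibration on 20 × log10(ratio) would leave a root mean square error of about 2.3 mmHg and limits of about ±4.4 mmHg, although the sensor itself has no error.

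The cost is analysis-plan wording and some programming, with no new data. With 25 patients the cross-validated limits will be wide. A single pooled calibration may also be blurred, because section 1.2 says the relation varies with acoustic pressure and settings are optimised for each patient.

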2.2.2 Secondary

We will use the results from the biopsy as the reference standard. The significance level of Generalized linear mixed logistic or GEE logistic modeling as well as the Mann-Whitney or Student's t-test will be 0.05.

3 Study Design

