4.1 Eligibility Criteria

4.1.1 Inclusion Criteria

Individuals must meet all of the following inclusion criteria in order to be eligible to participate in the study:

1. Provide signed and dated informed consent form
2. Be conscious, willing and able to comply with all study procedures and be available for the duration of the study
3. Female, at least 21 years old
4. Be scheduled for a breast biopsy (BIRAD 4, 4A, 4B, 4C or 5)
5. Patient with an at least 1 cm mass located at <3cm depth, approachable by 2.5 inch needle
6. Be medically stable as determined by the investigator
7. If a female of child-bearing potential, must have a negative urine pregnancy test within 24 hours prior to administration of Definity.

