11.1 Study Hypotheses

The main hypothesis is that the 3D subharmonic signals in the tumor and its surrounding tissue are correlated with the IFP values in them. The secondary hypothesis is that a marker from 3D subharmonic signals can predict the malignancy of breast tumor.

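### The logistic model that section 11.2 offers for malignancy has tissue site as its outcome, not biopsy result; the separate biopsy comparison is sound and should carry the conclusion

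*Combined protocol and SAP*

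**What the plan says.** The secondary hypothesis in section 11.1 is that "a marker from 3D subharmonic signals can predict the malignancy of breast tumor". For the secondary endpoint, section 2.2.2 states: "We will use the results from the biopsy as the reference standard". Its next sentence sets a 0.05 significance level for two analyses side by side: the mixed or GEE logistic model, and the Mann-Whitney or Student's t-test.

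Section 11.2 then describes both.

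- Logistic model (mixed or GEE), described in these words: "tumor vs. non-tumor samples will be used to explore the potential for using SHAPE results as a novel functional predictor". What is to be predicted is given as malignancy.
- Biopsy comparison: the subharmonic ratio from the tumor is set against the biopsy result as gold standard, tested by Mann-Whitney or t-test according to the distribution.

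The samples come from two regions of interest: "one within the tumor and the other in the surrounding tissues (available top and/or bottom region of tumor"). Eligibility in section 4.1.1 requires a mass ("Patient with an at least 1 cm mass located at <3cm depth") and that the patient "Be scheduled for a breast biopsy (BIRAD 4, 4A, 4B, 4C or 5"). Pathology is therefore unknown at entry, and every participant has a mass to sample.

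**The concern.** The logistic model is presented as evidence on malignancy, but the variable it predicts is whether a sample came from the mass or from the tissue around it. A benign mass is coded the same way as a cancer, and the biopsy result plays no part in the outcome. This does not fit section 2.2.2, which makes biopsy the reference standard and then attaches a significance level to the same model.

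Two errors could follow. If masses of any kind differ from their surroundings on SHAPE, the model will tend to be significant, and that result could be reported as prediction of malignancy. If only malignant masses differ, the benign masses coded as events weaken the apparent discrimination. Neither section says which of the two analyses decides the secondary objective, so nothing in the text prevents the site result from being used for it.

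**Working it through.** **1. What the outcome is.** Could *tumor* in section 11.2 mean malignant? Three places say no.

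- Section 1.1 counts benign tumors among the breast conditions whose pressure was measured.
- Section 11.2 sets tumor against healthy tissue in the agreement analysis.
- A mixed or GEE model is called for because each patient contributes both kinds of sample. Malignant versus benign is a single fact per patient.

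The outcome is therefore tissue site.

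**2. The plan's own figure.** The documents give no sample size or power for the malignancy analysis. The 19 to 29 patients in section 11.3 belong to the primary correlation. They reproduce with an exact two-sided 0.05 test at 80% power: n = 29 for r = 0.5 and n = 19 for r = 0.6. They do not bear on this point.

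**3. Can the site model be significant with no malignancy information?**

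- From the documents: 25 patients (3.2, 11.3), two sites each (11.2), significance level 0.05 (2.2.2).
- Assumed, because the documents give no values: one SHAPE value per site, normal with SD 1; a shift d added to every mass, benign or malignant alike; within-patient correlation ρ; malignancy independent of SHAPE, in 20% or 40% of patients or fixed at 10 of 25.
- Site model: logit P(sample is from the mass) = β0 + β1 × SHAPE, fitted by GEE with independence working correlation and robust standard errors, testing β1 = 0.
- Comparator: Mann-Whitney or t-test of the 25 mass values by malignancy.

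Share of simulated trials in which the site model gives p < 0.05 (ranges cover repeated runs):

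| Shift d | ρ = 0 | ρ = 0.5 | ρ = 0.7 |
|---|---|---|---|
| 0 | not tabulated | 5–6% | not tabulated |
| 0.5 SD | 39–42% | 64–69% | 82% |
| 0.8 SD | 76% | 97% | 99% |
| 1.0 SD | 90–93% | over 99% | 100% |

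The biopsy comparison rejected in 3% to 6% of trials throughout. Changing the malignant share from 20% to 40% made no material difference. With no shift the site model rejects at about its nominal level, so its significance follows the site difference alone.

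**4. Can it dilute a real signal?** Assume only malignant masses shift, by 1.5 SD, and 40% of masses are malignant. For normal values with equal SD, AUC = Φ(shift/√2).

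- Malignant versus benign: Φ(1.5/√2) = Φ(1.06) = 0.86.
- Mass versus surroundings: 0.4 × 0.86 + 0.6 × 0.5 = 0.344 + 0.300 = 0.64.

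The same appears in power. With a malignant-only shift of 1 SD, 40% malignant and ρ = 0.5, the site model was significant in 39% of trials, the Mann-Whitney test by malignancy in 59% and the t-test in 63%.

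**5. Precision of a patient-level AUC.** Use the Hanley-McNeil variance with A = 0.8, m cancers and k = 25 − m benign masses:

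Var = [A(1 − A) + (m − 1)(a − A²) + (k − 1)(b − A²)] / (mk), where a = A/(2 − A) = 0.667 and b = 2A²/(1 + A) = 0.711. Then a − A² = 0.0267 and b − A² = 0.0711.

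- m = 6, k = 19: (0.16 + 5 × 0.0267 + 18 × 0.0711)/114 = 1.573/114 = 0.0138; SE 0.117; 95% half-width 1.96 × 0.117 = 0.23.
- m = 12, k = 13: (0.16 + 11 × 0.0267 + 12 × 0.0711)/156 = 1.307/156 = 0.0084; SE 0.0915; half-width 1.96 × 0.0915 = 0.18.

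**The case against.** The strongest reply is that the plan already contains the right analysis. The sentence after the logistic model takes the tumor ratio, one value per patient, and compares it by biopsy result. This stands. A reader might infer from the logistic model that malignancy is never properly tested; section 11.2 shows otherwise, and that test keeps its error rate in the simulations above.

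A reader might also infer that the site model is the lead analysis because section 2.2.2 names it first. The documents do not support that. The two analyses are joined without ranking, and section 11.2 describes the logistic model as exploring potential. But an exploratory label does not turn a site outcome into a malignancy outcome, and section 2.2.2 still gives the model a significance level under the secondary endpoint.

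Third, the equal-shift scenario sits uneasily with section 1.1. There a cited study found a mean of 29 mmHg in invasive ductal carcinoma, against −0.3 to 3.6 mmHg in normal tissue, benign tumors and noninvasive carcinoma. If SHAPE follows pressure, benign masses may resemble their surroundings, and dilution becomes the likelier problem. That is fair. The documents neither give nor exclude a site shift from other causes.

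Fourth, it would go too far to say that the biopsy test offers no measure of prediction. The Mann-Whitney statistic divided by the product of the two group sizes is the AUC. What is missing is a commitment to report it, with an interval, whichever test is chosen.

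Finally, a random-intercept logistic model has no between-patient variation in outcome to estimate when each patient gives exactly one sample of each kind. This is correct but minor, because the plan allows GEE instead.

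**Conclusion.** The point holds for one of the two analyses listed under the secondary endpoint. The logistic model in section 11.2 is wrong as written: its outcome is tissue site, its stated use is malignancy, and this conflicts with biopsy as the reference standard in section 2.2.2. That conclusion rests on the text alone.

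The sizes are illustrative. With no malignancy information, the site model is significant in about 40% to 69% of trials at 0.5 SD and 90% to over 99% at 1 SD, for within-patient correlation 0 to 0.5, against about 5% for the biopsy test. In the dilution case the AUC is 0.64 instead of 0.86. The shift, correlation and malignant share are assumptions.

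This should be fixed, but it does not undermine the trial. The study is a 25-patient pilot sized for the primary correlation; the primary endpoint, safety and data collection are untouched, and a valid biopsy comparison is already planned.

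**What to change.** - **Section 11.2:** label the tumor versus non-tumor model *mass vs. surrounding tissue* and state that it is not evidence on malignancy.
- **Sections 2.2.2 and 11.2:** state that the malignancy conclusion rests on the patient-level comparison, with biopsy result (malignant or benign) as outcome and the tumor SHAPE ratio as predictor. Keep the planned Mann-Whitney or t-test and report the ROC AUC with a 95% CI beside it.
- **Any logistic model for malignancy:** use biopsy result as the outcome, one row per patient. Firth penalization and a tumor-minus-surrounding marker are optional; if the second marker is used, name it in advance.

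The cost is wording only, since biopsy results are already collected (sections 6.4 and 15.3). The drawback is 25 rows instead of 50 (25 patients × 2 sites, taking one value per site) and a wide interval: about ±0.18 to ±0.23 around an AUC of 0.8 with 6 to 12 cancers. That width shows what 25 patients can say about malignancy.
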